1.0 BACKGROUND AND RATIONALE

1.1 Review of the literature

Prevalence and incidence of delirium in advanced cancer

Delirium is a complex neuropsychiatric syndrome with fluctuating symptoms and multifactorial aetiology, characterized by a disturbance in cognition, arousal and attention occurring in the presence of an underlying medical condition.¹⁰ Delirium is associated with a spectrum of distressing symptoms (for example disorientation, sleep wake disturbance, hallucinations, delusions, agitation, paranoia, and worsening physical function).^{11,12}

The prevalence of delirium in patients with advanced cancer in both oncology and palliative care settings is significantly higher than that seen in other settings, including geriatrics. Delirium prevalence on admission to hospital in advanced cancer patients has been shown in several studies to range between 28% - 48%, and up to 90% in the days and hours before death. The reported incidence of new episodes of delirium during admission ranges between 20% and 45%. This means that two thirds of patients with advanced cancer may have a delirium episode at some point during an inpatient stay. The Australian Institute for Health and Welfare projected the number of deaths due to cancer in 2015 to be 46,570, so it is predicted at least 30,000 advanced cancer patients would have experienced delirium before their death.

There are multiple independent variables mediating this higher risk, such as advanced age, prior episode of delirium and cognitive impairment which all predispose to delirium in other settings; and also cancer-related factors such as hypoalbuminaemia, renal and hepatic impairment, bone and liver metastases, haematological malignancies, and use of opioids, corticosteroids and/or benzodiazepines. On average a person with cancer and delirium will have at least three contributing precipitants for delirium at any one time. When treated, delirium is reversible only in up to half of cases in advanced cancer.

Delirium is associated with significant morbidity and mortality

Delirium is one of the most significant medical complications in advanced cancer. Work by this team has confirmed that delirium is associated with increased mortality regardless of underlying illness. ¹⁹ This risk is increased if patients receive treatment with an antipsychotic, ²⁰ and extends after discharge even if delirium has resolved. ^{21,22} Even if detected and treated, delirium is associated with significant morbidity and economic cost arising from longer length of hospital stay, increased risk of functional and cognitive decline which often leads to a need for institutional care. ^{22,23} There is convincing evidence that people who experience delirium are aware of their symptoms and are highly distressed by the recollection of this when the delirium resolves. ²⁴ Delirium reduces mental awareness, when being mentally aware is highly valued by people with advanced cancer. ²⁵ Witnessing delirium is also highly distressing for families and health professionals. ²⁴ Treatment with

antipsychotics does not offer relief of symptoms in this setting, and delirium symptoms worsen after three days of treatment with either risperidone or haloperidol compared to placebo in a recent trial completed by this group.²⁰ Hence to make the most impact on outcomes delirium prevention is the key.

Current strategies for delirium prevention

Pharmacological; multicomponent non-pharmacological interventions; and proactive geriatric consultation have been evaluated for their potential to reduce the risk of delirium during hospital admission in at-risk patients outside the oncology setting.²⁶ Despite the significance of delirium in cancer, there are no studies available to inform specific guidance for the cancer setting.

Pharmacological strategies have included anticholinesterases, atypical and typical antipsychotics, tested in heterogeneous post-operative settings.²⁷ Comparators for these agents have been placebo or, in one study, proactive geriatric consultation.²⁶ Antipsychotics may reduce delirium incidence and duration²⁸, but further trials are necessary before clinical recommendations can be made due to heterogeneity of populations, doses and agents studied, and methodological concerns in some studies (incomplete follow-up, poor delirium case identification, underpowered).²⁷

Non-pharmacological strategies (e.g. physical and cognitive exercise) for delirium prevention have been explored in eleven interventional studies. A recent meta-analysis (n=4,267) of randomized or matched trials showed significant reduction in delirium incidence, with the odds of delirium 53% lower in the group receiving non-pharmacological interventions compared with controls (odds ratio 0.47, 95% confidence interval 0.38-0.58, p<0.001). However, less than a third of the included studies were RCTs, blinding was difficult to achieve due to the nature of the interventions, and many of the included studies had small sample sizes. A RCT of proactive physician-led geriatric consultations following hip fractures also showed reduced delirium incidence.

The challenge is that 'one size' does not fit all, with components of cognitive and exercise interventions not feasible for many patients with advanced cancer, who experience high levels of fatigue and/or functional decline. Advanced cancer patients are therefore unlikely to sustain the intervention over time as cancer progresses, corresponding to the period of highest probability of delirium. A less challenging multicomponent intervention developed for advanced cancer patients failed to demonstrate a difference in the incidence of delirium between two palliative care centres that received the intervention and seven that did not.³² There are also significant issues in translating multi-component interventions into practice that require substantive administrative changes,³³ as well as comprehensive and ongoing clinician education; with upfront additional costs estimated as AUS\$800/patient (though a delirium episode can cost the healthcare system up to AUS\$90K (2005 figures)).³⁴

1.2 Existing evidence

Melatonin Physiology and pharmacokinetics

Melatonin (N-acetyl-5-methoxytryptamine) is a hormone produced by the pineal gland and secreted in response to darkness. High levels of melatonin are present at night whilst it is almost absent during the daytime. Night-time production of melatonin is driven by the hypothalamic suprachiasmatic nucleus (SCN) and a feedback system to this internal clock results in sleep onset/sleepiness. This chronobiotic property of melatonin and light/dark exposure maintains circadian rhythms and regulates the sleep-wake cycle.³⁵ Melatonin is metabolised from serotonin, which is derived from trypophan. ³⁶ Tryptophan is first converted to 5 – hydroxytryptophan by tryptophan hydroxylase, and then decarboxylated to serotonin which is then metabolised to melatonin by two enzymes located in the (arylalkylamine pineal gland N-acetyltransferase and hydroxyindole-Omethyltransferase) 37

Evidence for the role of melatonin in delirium prevention

Current theory of delirium pathophysiology: Though it was previously believed delirium was mediated by dopamine and cholinergic abnormalities alone, many neurotransmitter pathways are now implicated.³⁸ There are complex interactions between the circadian system and the other pathways involved in causing delirium – namely the cholinergic, dopamine, GABAergic systems and hypothalamic-pituitary-adrenal axis.³⁹ Inflammatory mechanisms also play a significant role in delirium, with delirium believed to be an outward expression of potentially reversible brain inflammation triggered by peripheral immune stimulation. The SCN also exerts a circadian influence on the inflammatory response via melatonin.³⁹

Evidence of melatonin deficiency in delirium: Chemical or inflammatory processes in delirium may disrupt signalling pathways and function of the SCN and pineal gland. Changes in hepatic enzyme activity and reduced oral intake may also stimulate enterochromaffin cells to produce melatonin, contributing to raised levels occurring at the wrong time, leading to circadian desynchrony. Tryptophan depletion also occurs in illness, which can lead to melatonin deficiency ("Tryptophan dysregulation model"). Low tryptophan levels are seen postoperatively and low melatonin levels have been reported in both postoperative and intensive care units (ICU) setting where delirium is also prevalent. Lack of circadian rhythm rise with persistently low serum melatonin levels has been reported in ICU patients with delirium. Finally, it is possible that melatonin regulation is altered by psychoactive medications commonly used in palliative care. Opioids increase melatonin secretion, benzodiazepines may impair light induced phase shifts of circadian rhythms and corticosteroids have a suppressive effect.

1.3 Rationale for intervention

Clinical evidence for efficacy of melatonin in delirium prevention:

Preliminary work supports the need to explore the role of melatonin in delirium prevention further, particularly in cancer or palliative populations where no data exist. Three investigator-led RCTs in elderly populations and a phase II RCT by this team in cancer patients demonstrate preliminary evidence for a role for melatonin in delirium prevention, with all studies showing a positive effect on preventing delirium or reducing its duration, as well as encouraging safety profile. A RCT of elderly patients admitted to hospital through emergency (n=145) found daily 0.5 mg melatonin over 14 days prevented delirium (OR 0.29 (95% CI: 0.11–0.74)). 49 Only two adverse events were reported, and neither were directly attributed to melatonin. 49

A RCT of 300 participants aged >65 years undergoing hip arthroplasty under spinal anaesthesia randomized to one of 4 groups: Group 1 (control) received no sedation; Group 2 (melatonin) received 5 mg melatonin at bedtime and 5mg melatonin 90 minutes preoperatively; Group 3 (midazolam) received 7.5 mg midazolam 90 minutes preoperatively and Group 4 (clonidine) received 100 mcg clonidine at sleep time and another 100mcg 90 minutes preoperatively. 50 There was a significant reduction in postoperative delirium defined as Abbreviated Mental Test Score <8 in those administered melatonin (event rate 5/53 melatonin (2% of all delirium episodes) versus 16/49 control (9% of all delirium episodes)), with a non-statistically significant increase in delirium in clonidine (event rate 19/51, 11 of all delirium episodes) and midazolam (22/50, 14% of all delirium episodes) groups. Patients from any group in this RCT who developed postoperative delirium (62/300) went on to a further trial to evaluate melatonin for delirium treatment. These patients received 5 mg of melatonin at 9 pm for three successive days in a trial to treat delirium, and in this group treatment was deemed successful in 58% of cases, though the treatment success definition was not described.⁵⁰ These results are limited by a cognitive test rather than validated delirium instrument being used for the primary outcome, adverse effects not reported, being underpowered and lack of a response definition.

A RCT of melatonin (3mg for five consecutive days from 24 hours of admission) for the prevention of delirium in elderly hip fracture patients in the Netherlands (n=452), observed no effect on delirium incidence, however demonstrated a reduction in delirium duration, with fewer patients in melatonin group experiencing a delirium episode lasting for over two days (25% vs 54%, p=0.02). Another near-complete Canadian study is underway of melatonin (5mg) for 5 postoperative days (n=302) in patients undergoing elective vascular or cardiac surgery (NCT01198938).

The melatonin agonist, ramelteon 8mg/day, has also shown benefit in the elderly medically unwell (n=69) with lower risk of delirium (3% compared with 32% in placebo group, p=0.003, which was still seen even after controlling for other risk factors (odds ratio 0.07, 95% CI 0.008-0.54, p=0.01)⁵² Melatonin, bright light therapy

and melatonin agonists have also been used successfully to treat delirium, further supporting a benefit.³⁹

Melatonin offers promising potential as a safe pharmacological agent for preventing delirium. Due to the differing baseline risk factors, multiple clinical precipitants and the higher prevalence in cancer it is important to evaluate whether similar effects are seen in this setting.

1.4 Conclusions and aims

This is the first trial of its kind in cancer care, aiming to prevent delirium, or reduce its duration and severity to stall the cascade of functional and cognitive decline, morbidity, mortality and resultant health care costs. Melatonin use could be rapidly translated into practice, given the formulation already has Therapeutics Goods Administration registration for another indication.

1.5 Rationale and significance

Delirium is one of the most significant medical complications in advanced cancer. Work by this team has confirmed that delirium is associated with increased mortality in advanced cancer, ¹⁹ a risk that is increased if patients receive treatment with an antipsychotic, ²⁰ and extending after discharge even if delirium has resolved. ^{21,22} Even if detected and treated, delirium is associated with significant morbidity and economic cost arising from longer length of hospital stay, increased risk of functional and cognitive decline which often leads a need for institutional care. ^{22,23} People with cancer who experience delirium are aware of their symptoms, are highly distressed at the time and when recalling after delirium resolves. ²⁴ Delirium reduces mental awareness, when being mentally aware is highly valued by people with advanced

cancer.²⁵ Witnessing delirium is also highly distressing for families and health professionals.²⁴ Treatment with antipsychotics does not offer relief of symptoms in this setting, with delirium symptoms worse after three days of treatment with either risperidone or haloperidol compared to placebo in a recent trial completed by this group.²⁰

2.0 STUDY OBJECTIVES

2.1 Aim

The principal aim of this investigator-initiated, cooperative group trial is to determine the effectiveness of melatonin in preventing delirium; by increasing the number of delirium-free days during hospital admission, achieved by reducing overall delirium occurrence, or reducing duration and severity of delirium if it occurs.

2.2 Objectives

2.2.1 Primary objective

The primary objective is to determine if oral prolonged release melatonin when compared to placebo can increase the number of delirium-free days during a hospitalisation for advanced cancer patients.

2.2.2 Secondary objectives

Secondary objectives are to determine if oral prolonged release melatonin can:

- 1. reduce delirium severity and duration for those who develop a delirium episode;
- 2. reduce delirium incidence;
- 3. cause adverse effects, in particular sedation;
- 4. positively influence adverse events associated with delirium episodes, including:
 - vi. length of hospital stay and inpatient resource utilisation;
 - vii. benzodiazepine and antipsychotic use (delirium or non-delirium indication);
 - viii. in-hospital complications (pressure areas, falls, thromboembolism, pneumonia, functional decline);
 - ix. days spent in coma and survival;
 - x. Patient and family distress;
- 5. provide other symptom benefits in the form of improved sleep quality.

2.3 Null Hypothesis

The null hypothesis is that oral prolonged release melatonin 2mg will not result in an increased number of delirium-free days for people with advanced cancer compared to placebo during an inpatient stay, when used in conjunction with non-pharmacological preventative strategies.

3.0 STUDY POPULATION

3.1 Target population

Adult advanced cancer patients admitted to hospital without delirium

3.2 Inclusion criteria

- Aged 18 years or older
- English speaking or availability of a health care interpreter.
- Diagnosis of advanced cancer (histological or clinical diagnosis) defined by the intent of treatment no longer being curative
- Admission to an acute or sub-acute inpatient facility
- participant is able to give fully informed written consent

3.3 Exclusion criteria

[figure not shown]
- Inability to take medications orally
- Delirium on admission as defined the cut off score on the delirium rating scale DRS-R-98⁵⁴ ≥17.75 indicative of delirium
- Australian Karnofsky Performance Status (AKPS) score less than 30 at the beginning of the study;
- A known allergy to melatonin or placebo content
- Active seizure disorder defined as seizure within last one month, or seizure disorder not on anticonvulsants
- Concomitant cimetidine use (CYP2D Inhibitor increases melatonin levels by 1.7 fold)
- Current history alcohol abuse (alcohol reduces melatonin levels);
- In people taking warfarin, a markedly nontherapeutic international normalized ratio (< 1 or > 4)
- Moderate to severe dementia as defined by clinical diagnosis of dementia and a Short Blessed Test (SBT) score of ≥10
- Severe hepatic impairment (defined as bilirubin ≥2.5 times upper limit of normal; alkaline phosphatase, aspartate transaminase and/or alanine transaminase > 3 times upper limit of normal clinically determined to be due to hepatic impairment)
- Current use of melatonin for other indication, melatonin use within last 14 days
- Currently taking agomelatine, or use of agomelatine in the past 7 days
- Pregnant or breastfeeding

4.0 INVESTIGATIONAL PLAN

4.1 Study design

A prospective, randomised, double-blind, placebo-controlled parallel-arm, multicentre phase III trial of oral prolonged release melatonin 2mg versus placebo taken each night during inpatient oncology or palliative care admission.

4.2 Study diagram

*Standardardised non-pharmacological prevention protocol in both arms: for reducing delirium risk (targeting sleep preservation, mobility, orientation and sensory deficit minimisation) and to standardise light exposure at night.

5.0 INTERVENTIONS

5.1 Study medication

Arm 1: Oral melatonin prolonged release 2mg (Neurim Pharmaceuticals Ltd) taken at 2000 +/-hours. Intervention will be commenced within 48 hours of admission and continued until delirium occurrence, discharge or for a maximum of three weeks if patient remains in hospital (e.g. while awaiting long-term care placement) after any acute medical issues imparting a delirium risk have been resolved.

Arm 2: Oral placebo tablet containing identical ingredients except the active ingredient melatonin

5.2 Dosing schedule

All study drug will be prescribed as a daily dose to be taken at 2000 (+/- one hour) of each day of the intervention period.

Rationale for dose and timing of administration:

The optimal timing of melatonin is two hours before bedtime, with this timing used in prior studies. 49 Doses used in prior delirium prevention studies ranged from 0.5 to 5mg. 49 September 2016 24 of 80

Lower doses provide sufficient increment of serum melatonin levels, and higher doses are associated with sustained daytime supra-physiological melatonin levels with a study in critical care demonstrated that a 10mg dose is excessive. ⁵⁵ Oral melatonin 2mg prolonged release is the only Therapeutics Goods Administration (TGA) approved formulation in Australia, the dose proposed is within the range of prior studies. This dose and timing has demonstrated a signal of effect in our pilot phase II study.

5.3 Method of assigning participants to treatment groups

At each centre, people referred to the study will be sequentially allocated an ID number. This ID number will be used for all subsequent study documentation for that participant. The procedures outlined in the Allocation of ID number Standard Operating Procedure (5.5.5 Allocation of ID number) are to be followed.

Randomisation schedules will be developed for each site using random number tables, generated at an independent central registry. Randomisation will be conducted using permuted block randomization with a block size between 3 and 6. The randomization will be conducted using a computer algorithm. The central registry will supply site randomisation schedules to each site pharmacy. There will be no stratification at the randomisation level for this study.

On notification of a participant, the pharmacist at each site will consult the supplied randomization schedule and will allocate the next code available. The participant ID, allocation code, dates of request, preparation, and dispensing will be recorded in a log maintained by the pharmacist and supplied to the central registry on each randomisation.

At all times, from eligibility screening to completion of the study, all study staff are unaware of the treatment allocation. Allocation is concealed from the investigator at the time of the participant inclusion in the trial; the allocation is determined by contacting the site pharmacy.

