11.2 Statistical analysis of efficacy primary outcome

Intention-to-treat analysis will be used for all statistical comparisons. For the primary outcome, comparisons between groups for delirium-free days, with adjustment to the length of stay and other potential covariates using a general linear model approach will be undertaken. For potential missing data, multiple imputation technique will be applied to handle the missing data. A proper multiple imputation method will be employed that based on various models of assumption including missing completely at random (MCAR), missing at random (MAR), and missing not at random (MNAR). Sensitivity analysis will apply to examine the effects of these different assumptions on the imputed data structure in order to ascertain the most reliable approach.

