11.5 Power and sample size

Sample size was calculated based on the information obtained in the pilot study on the primary outcome, namely delirium-free days during a 3 week study period, and an analytical approach of comparing the mean delirium-free days between groups. It has been estimated that a sample size of 110 in each arm (n=220 in total) would provide 90% power to reject the null hypothesis with a 5% type I error rate to detect an increase of 2 delirium-free days allowing for 30% drop out or loss to follow-up and 5% for possible adjustments for covariates.

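### Section 5.3 permits odd block sizes in a 1:1 trial and calls per-site blocked schedules unstratified; the effect is small, but the specification needs correcting before schedules are generated

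*Protocol*

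**What the plan says.** Four places in the protocol bear on this.

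- **Section 4.1** describes a "double-blind, placebo-controlled parallel-arm, multicentre phase III trial of oral prolonged release melatonin 2mg versus placebo", so there are two arms.
- **Section 5.3** covers the randomisation. On blocks: "Randomisation will be conducted using permuted block randomization with a block size between 3 and 6". On schedules: "Randomisation schedules will be developed for each site using random number tables, generated at an independent central registry". The registry then supplies each site pharmacy with its own schedule, and the site pharmacist takes the next code from it. On stratification: "There will be no stratification at the randomisation level for this study". No allocation ratio is given.
- **Section 11.5** plans "a sample size of 110 in each arm (n=220 in total"). This is the only source for the ratio, and it implies 1:1.
- **Section 11.2** sets out the primary comparison "with adjustment to the length of stay and other potential covariates using a general linear model approach will be undertaken". Site is neither named nor excluded.

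**The concern.** Two statements in section 5.3 do not fit the rest of the design.

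First, a permuted block balances two equal arms only if its size is even. The stated range lets in odd sizes, and the text is silent on how the odd place is assigned. A schedule that tilts odd blocks at random and one that always tilts them towards the same arm would both comply with the protocol, yet they give different overall allocations.

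Second, an independent permuted-block list for each site is stratification by site. A flat denial of stratification in the same section misdescribes the design. An analyst who reads that sentence alone would not know that site is a design factor.

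What is at stake is tightness of balance, within sites and overall, and a correct record of how patients were randomised. Allocation remains random under any of these schemes, so the validity of the comparison is not in question.

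**Working it through.** **1. The plan's own figure.** Inputs from section 11.5: "would provide 90% power to reject the null hypothesis" and "with a 5% type I error rate to detect an increase of 2 delirium-free days", with allowances of 30% for drop-out and 5% for covariates. The test is taken as two-sided (not stated). Section 11.5 gives no SD; section 1.2/1.3 reports pilot SDs of 3.7 (melatonin) and 6.4 (control). With SD 3.7:

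- n per arm = 2 × (1.960 + 1.282)² × 3.7² / 2² = 71.9, so 72.
- 72 / (0.70 × 0.95) = 108.3, so 109; 72 / 0.65 = 110.8, so 111.

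This reproduces 110 per arm to within rounding, with equal arms. Of the SDs tried, only 3.7 does so, and it is used below for that reason.

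**2. Parity.** A block of 3 splits only 2:1 and a block of 5 only 3:2. Read inclusively, the range is 3, 4, 5, 6; read exclusively, it is 4, 5. Odd sizes are admitted either way. If the admitted sizes are equally likely (assumed), half of all blocks are odd and the mean block size is 4.5 under both readings.

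**3. Extra place assigned at random.** Allocation is 1:1 in expectation. About 220 / 4.5 = 48.9 blocks are needed, of which 24.4 are odd. Each odd block adds +1 or −1 to the arm difference, so completed odd blocks alone give an SD of √24.4 = 4.9; unfinished blocks add to that. Simulation of 220 patients (1,500 runs, sites with equal expected recruitment; the number of sites is not stated, so 5 and 12 were assumed) gives:

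| Block sizes | Sites | SD of arm difference | 95th percentile |
|---|---|---|---|
| 4, 6 | 5 | 2.3 | 4 |
| 4, 6 | 12 | 3.5 | 6 |
| 3, 4, 5, 6 | 5 | 5.4 | 10 |
| 3, 4, 5, 6 | 12 | 5.8 | 12 |
| 4, 5 | 5 | 5.3 | 10 |
| 4, 5 | 12 | 5.9 | 12 |

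The largest imbalance at any one site averages 3.7 patients with sizes 3 to 6, against 1.5 with sizes 4 and 6 (5 sites). With 12 sites the figures are 3.3 and 1.9.

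**4. Extra place always to the same arm.** The share of that arm is (2 + 2 + 3 + 3) / (3 + 4 + 5 + 6) = 10/18 = 5/9, or (2 + 3) / (4 + 5) = 5/9 on the exclusive reading. Of 220 patients that is about 122 against 98.

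**5. Power.** Evaluable patients: 110 × 0.70 × 0.95 = 73.15 per arm, 146.3 in total. Power = Φ(2 / SE − 1.96), with SE = 3.7 × √(1/n₁ + 1/n₂).

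- Equal arms: SE = 0.612, power 90.5%.
- 5/9 to 4/9 (81.3 v 65.0): SE = 0.616, power 90.1%.
- Extreme, every block of size 3 and tilted to one arm (2/3 to 1/3, about 147 v 73 randomised): SE = 0.649, power 86.9%.

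The relative efficiency is 4p(1 − p) whatever the SD: 4 × (5/9) × (4/9) = 0.988 for the systematic tilt. At an arm difference of 12 the loss is (12/220)² = 0.3%.

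**The case against.** The strongest reply is that very little follows. The protocol gives a range, not a list, and a registry using only 4 and 6 would comply with it if the range is inclusive. If odd sizes are used, each completed block is out by only one, whereas an unfinished block of 6, which an even-block scheme keeps, can leave a site out by three. The power cost is a fraction of a percentage point. On stratification, the per-site schedules are described openly, so nobody carrying out section 5.3 would act differently; the natural reading is that no patient factors are used.

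Most of this stands as to size. A reader might infer that odd blocks defeat the purpose of blocking or cost the trial meaningful power. The figures do not support that: balance is loosened, not lost. It does not stand as to wording. The text also permits the odd sizes and leaves the tilt open, and the sentence on stratification says something other than what its authors probably meant.

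A reader might also infer that site has been left out of the primary analysis, with a loss of precision. The documents do not establish this. Section 11.2 leaves the further covariates open, section 11.5 budgets for covariate adjustment, and a statistical analysis plan, which is not at hand, commonly holds the list. Nor does any figure in the protocol say how much of the outcome variance lies between sites.

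**Conclusion.** The point holds as an error of specification with a small numerical effect. Section 5.3 admits block sizes that cannot be balanced in the 1:1 design of section 11.5, does not say how the odd place is assigned, and denies a stratification that it sets up itself.

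With random tilt, the 95th-percentile arm difference roughly doubles, from 4–6 to 10–12 of 220. With systematic tilt, the split is about 122 to 98 and power falls by 0.4 percentage points. These figures assume equally likely block sizes and, for the simulated differences, 5 or 12 sites of similar size. The power figures assume a two-sided test and SD 3.7. The case for acting rests on correctness and on timing, since an allocation schedule cannot be mended after use. It does not rest on lost power.

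**What to change.** In section 5.3:

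- State that allocation is 1:1, in permuted blocks of randomly varying even size. The exact sizes (4 and 6, for example) can be held by the central registry and kept out of a document that every site holds.
- Replace the sentence on stratification with a statement that randomisation is stratified by site, with no stratification by patient factors.

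As an accompanying change, name site among the covariates in section 11.2, because it is the factor used to randomise. Small sites would need to be pooled, or site fitted as a random intercept.

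The cost is one instruction to the registry before schedules are generated, two sentences in section 5.3 and one model term. The sample size stays at 110 per arm. If any schedule has already been issued, record the block sizes and the rule for the odd place that were actually used.
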